Visit Timepoint / Window	Up to 45 days		2-3 days post Epi	+/- 2 Days	30 days +7	91-121 days post Epi	1 day post Endo	7 days post Endo +1	30 days post Endo +7	90 days +14	180 days +/- 30	Symptom or Test	365 days + 30	Year +/- 60 days	Approx. 6 Mo post Annual Visit	Exit
Primary Effectiveness Endpoint														X		
Telephone Contact				X ²⁴				X							X	
Occurrence of AF/AFL/AT – Health Economic Endpoints														X	X	
Study Exit																X

¹ See **Subject Visits** for tests to be conducted at each visit.

² Anticoagulation testing to be performed in accordance with institutional SOC depending on subject's anticoagulation therapy.

³ LAA exclusion verification only for subjects that had the AtriClip placed during Epicardial Surgical Ablation Procedure. These data are submitted to a core lab.

⁴ AF Classification Form must be completed and submitted to sponsor for review prior to Epicardial Surgical Ablation Procedure

⁵ Urine or serum pregnancy test - females of childbearing potential (**within 7 days prior to the surgical procedure**).

⁶ Collection/analysis completed within 7 days of procedure.

⁷ Must be conducted within 120 days prior to the Epicardial Surgical Ablation Procedure.

⁸ In subjects with a documented history of pulmonary compromise.

⁹ Must be conducted within 60 days prior to the Epicardial Surgical Ablation Procedure.

¹⁰ Anticoagulation/antiplatelet therapies administered per SOC.

¹¹ Intraoperative confirmation that no clot is present in LAA.

¹² CT/MR Imaging performed only if subject exhibits symptoms suggestive of pulmonary vein stenosis. Use same imaging technique performed at baseline imaging to the extent possible.

¹³ Only health status will be collected.

¹⁴ For example, cardioversion for subjects in atrial fibrillation per physician discretion.

¹⁵ A Holter or Zio™ Patch will be worn by all subjects.

¹⁶ Conducted prior to surgical procedure to rule out LA/LAA thrombus and post LAA management to confirm exclusion of LAA.

¹⁷ See **Subject Visits 12-15** for details of events of interest to be collected.

¹⁸ CTA imaging of the LAA performed only in those subjects that had the AtriClip placed during the Epicardial Surgical Ablation Procedure. Pulmonary veins will also be

CONFIDENTIAL

Protocol Number: CP-2014-1

Protocol Name: DEEP Pivotal

Version: Rev H; 11May2021

Page 21 of 129

assessed, and CTA will be utilized.

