5.1.6 Left Atrial Appendage (LAA) Exclusion

The left atrial appendage should be managed using the AtriClip PRO (PRO1 or PRO2) device. Only if the surgeon deems that the AtriClip Pro device is not able to be utilized for Left Atrial Appendage exclusion because of anatomical limitations, the surgeon may utilize a stapling device in accordance with surgical standard of care (SOC). If the surgeon determines it is not feasible or safe to address the LAA, the appendage may be left intact.

General Placement of the AtriClip PRO:

The PRO1 is introduced into the chest through the incision (the PRO2 fits through a trocar) at the 6th or 7th intercostal space directing it toward the base of the Left Atrial Appendage. Using soft endoscopic forceps or a Kitner in the surgeon’s right hand, the open AtriClip device is passed over the tip of the left atrial appendage. The tip of the appendage is gently teased into the AtriClip. The device is then lowered into the base of the appendage. The skillful manipulation of the endoscope will allow the surgeon to see all angles and visualization surrounding structures and assess whether the appendage is fully contained within the AtriClip. Awareness of the proximity of the circumflex artery and its relationship to the targeted location at the base of the left atrial appendage is critical. Using the transesophageal echo (TEE) to help guide placement, the AtriClip is applied on the left atrial appendage ensuring the alignment and complete closure of the LAA. Refer to the IFU for proper AtriClip size selection.

AtriClip Deployment at Base of LAA

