The surgeon should introduce a stapling device and carefully position it around the base of the LAA. Using the transesophageal echo (TEE) to help guide placement, the stapler is closed on the base of the atrial appendage and it is amputated. The amputated LAA is withdrawn from the stapler. A TEE should be performed to evaluate the base of the LAA along the entire length and depth of the excluded appendage. If it is determined that exclusion is not complete (i.e., there is blood flow between the LAA and the LA at any point), additional thoracoscopic methods such as sutures or clips may be used to exclude the LAA completely.

Closure & Epicardial Procedure Completion

The pericardium may be re-approximated with a single suture using a laparoscopic suturing device such as the commercially available Endo Stitch™ device. If closure of the pericardium seems to be putting any tension on the deployed AtriClip, this step is not performed. A chest tube is placed, the lung inflated and visualized. The ports are then withdrawn. The subject should be ventilating both lungs effectively. Sterile dressings are applied.

Restoration of Sinus Rhythm

If the subject is not in sinus rhythm at the end of the epicardial surgical procedure, electrical cardioversion may be performed, at the discretion of the surgeon, understanding that these subjects are not typically anticoagulated at this time. The subject is then transferred to the post-operative care ward.

Post Epicardial Surgical Procedure - Subject Assessment

To assess the subject status with regard to potential bleeding, assessments of hemoglobin and

hematocrit shall be performed post-surgical ablation procedure.

Esophagoscopy

An esophagoscopy must be conducted and/or obtained **between 24-72 hours** following the Epicardial Surgical Ablation Procedure. (Refer to Protocol Section 7.0 Subject Visit 3 for details.)

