9.6 Secondary Endpoints

9.6.1 Secondary Endpoints – Effectiveness

For labeling purposes, to be tested if the primary effectiveness endpoint is a success:

1. Exclusion of the LAA, defined as defined by lack of fluid communication (<3 mm residual communication with LAA and < 10mm residual pocket) between the LA and LAA. This endpoint will be measured at the 12-Month (Visit 11) (approximately 15 months post AtriClip placement). The AtriClip effectiveness population will be utilized for analysis of this endpoint.

Based on a literature review of peer-reviewed research that was performed for the EXCLUDE trial (add reference here for the trial), a weighted average rate of 77.5% exclusion at 3 months was derived as a reasonable expectation of success, based on a combination of cut and sew and stapling procedures³⁵⁻⁴⁴. That same trial resulted in actual exclusion rates of 95.7% (67/70) for intra-procedural success and 98.4% (60/61) for 3-month success. Utilizing the most conservative of these results gives a 95% lower confidence limit of just under 88% for an exact binomial confidence interval.

In the current study, it is believed that the placement of a clip will provide a significant benefit to the patient with extremely low added safety risk. A success rate of over 80% will exceed the 77.5% expectation of success based on other exclusion methods, with less risk of injury than those methods³⁵⁻⁴⁴, and is a reasonable expectation based on the EXCLUDE results that showed a lower bound of just under 88%. The associated hypothesis test, based on an exact binomial confidence interval, will be as follows:

$$H_o : p_2 \leq .80 \quad vs. \quad H_a : p_2 > .80$$

Exploratory endpoints:

2. Exclusion of the LAA, defined as lack of fluid communication (<3 mm residual communication with LAA and <10 mm residual pocket) between the LA and LAA. The endpoint will be measured intra-procedurally (Visit 2), and at the Endocardial EP Ablation Procedure (Visit 5). The AtriClip effectiveness population will be utilized for analysis of this endpoint.
3. Acute procedural success of surgical epicardial procedure, defined as the percentage of subjects with successful electrical isolation/block of all pulmonary veins, as well as the “box”. The ITT and PP populations will be utilized for analysis of this endpoint.

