5.2 Analysis Populations

Intent to treat patient population (ITT): The ITT subject population will include all subjects who have met all inclusion/exclusion criteria and on whom a procedure was attempted (defined as a subject who underwent induction of anesthesia).

Modified intent to treat patient population (mITT): The mITT subject population will include all subjects who attempted the Epicardial Procedure (defined as a subject who underwent induction of anesthesia) and have at least one post-procedure follow-up visit after the 2nd Blanking Period (with the 2nd blanking period defined as the 90-days post Endocardial Ablation Procedure) with non-missing primary effectiveness data.

Safety Population: The safety population will include all enrolled subjects that undergo induction of anesthesia.

Per protocol patient population (PP): The PP patient population will include all subjects who complete both the Epicardial Surgical Ablation Procedure and Endocardial EP Ablation Procedure.

AtriClip Effectiveness population: The AtriClip effectiveness population will include all ITT subjects for whom an attempt (entrance of the AtriClip into the chest wall) is made to place an AtriClip device.

The primary effectiveness analysis will utilize the mITT patient population as defined in this statistical analysis plan. The analysis will be repeated on the ITT and PP patient populations as supportive analyses. Secondary effectiveness analyses will be conducted on the mITT, the ITT and the PP patient populations. All safety analyses will utilize the safety population.

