5.6.3.1 Secondary Effectiveness Endpoint #1

The statistical analysis of secondary effectiveness endpoint #1 will consist of a comparison of the proportion of patients with LAA exclusion at the 12 Month Visit is statistically significantly higher than 80%, which will exceed the 77.5% expectation of success based on other exclusion methods, with less risk of injury than those methods. The primary effectiveness endpoint will be assessed with the following hypothesis:

$$H_0: p_2 \leq 0.80$$

Statistical Analysis Plan		Page 15 of 22
Sponsor	Study	Version
AtriCure	DEEP Pivotal Study	Version 2.0

$$H_a: p_2 > 0.80$$

where p_2 = the proportion of subjects with LAA exclusion at the 12-month Visit. LAA exclusion is defined as a lack of fluid communication (<3 mm residual communication with LAA and < 10mm residual pocket) between the LA and LAA. The hypothesis will be evaluated using a one-sided statistical test. An exact, one-sample binomial test will be conducted at a one-sided $\alpha=0.025$ level of significance to test the hypothesis. The objective will be met if the estimated one-sided p-value is < 0.025. The AtriClip effectiveness population will be the primary population for this analysis. The LOCF method will be utilized for patients who do not have TEE testing at the 12-Month visit.

The proportion will be calculated with subjects as the experimental unit. The numerator of the proportion will be the number of subjects with LAA exclusion at the 12-month Visit and the denominator will be the total number of subjects. The endpoint will be presented with the numerator and denominator, the proportion and its 95% two-sided exact binomial confidence interval, and the one-sided p-value.

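### LAA exclusion endpoint #1 keeps failed AtriClip attempts in the denominator but does not require that an AtriClip achieved the exclusion, so a stapled closure can count as an AtriClip success

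*SAP*

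**What the plan says.** **Population.** SAP 5.2 and Protocol 9.5 define the AtriClip effectiveness population by attempt: "The AtriClip effectiveness population will include all ITT subjects for whom an attempt (entrance of the AtriClip into the chest wall) is made" to place the device. Nothing is said about whether the clip stays in place.

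**Crossover.** Protocol 5.1.6 permits a stapler only where the surgeon judges that anatomy prevents use of the AtriClip. After stapling, "A TEE should be performed to evaluate the base of the LAA along the entire length and depth of the excluded appendage". If closure is incomplete, "additional thoracoscopic methods such as sutures or clips may be used to exclude the LAA completely".

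**Scoring.** SAP 5.6.3.1 defines exclusion by anatomy alone (under 3 mm residual communication and under 10 mm residual pocket). "The numerator of the proportion will be the number of subjects with LAA exclusion at the 12-month Visit", and the denominator is all subjects in the population.

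**Imaging.** Footnote 3 to the Schedule of Assessments reads: "LAA exclusion verification only for subjects that had the AtriClip placed during Epicardial Surgical Ablation Procedure". Footnote 18 and Protocol 7.14 limit the 12-month LAA CTA in the same way.

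**Missing data.** SAP 5.6.3.1 states: "The LOCF method will be utilized for patients who do not have TEE testing at the 12-Month visit". SAP 5.3 and Protocol 9.8 and 9.9 also assign LOCF to this endpoint.

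**Status.** Protocol 9.6.1 lists endpoint #1 alone for labeling, tested if primary effectiveness succeeds. SAP 5.6.3 makes the other secondary effectiveness endpoints exploratory.

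**The concern.** An attempt-based population normally serves to charge failed placements to the device. That works only if a failed placement is scored as a failure, and neither document says so. The footnotes speak of subjects in whom the clip was placed, while the population speaks of attempts, so the plan itself leaves room for subjects who were attempted but not placed.

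For such a subject the error can run only in the device's favour: a placement failure becomes an exclusion success. The comparison is also blurred. The 80% goal is justified as exceeding a 77.5% benchmark that is "based on a combination of cut and sew and stapling procedures" (Protocol 9.6.1), so one of the benchmark techniques could be counted on the AtriClip side. At stake are the error rate of a labeling test and the meaning of the exclusion rate reported for the device.

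**Working it through.** **1. The plan's own figure.** Protocol 9.6.1 cites 67/70 = 95.7% intra-procedural exclusion in the earlier AtriClip trial, with a 95% exact lower limit of just under 88%. The two-sided 95% Clopper-Pearson lower limit for 67/70 is 0.8798. The figure reproduces.

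**2. The path of one subject.**
- The clip enters the chest, so the subject is in the population (SAP 5.2).
- Anatomy prevents its use and the LAA is stapled (Protocol 5.1.6).
- A TEE after stapling shows exclusion (Protocol 5.1.6 and 7.2).
- No 12-month LAA CTA is planned, because no AtriClip was placed (footnotes 3 and 18; Protocol 7.14).
- The 12-month value is absent and LOCF applies. The last reading is the Visit 2 TEE, or a Visit 5 TEE if one was done. Either reading reflects the stapler.
- No text scores the subject as a failure, so the subject can enter the numerator.

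**3. Size of the exact test.** Inputs: null 0.80, one-sided 0.025, exact binomial (SAP 5.6.3.1). The documents give no sample size for this test. N=220 is the maximum treated (Protocol 9.3); N=200 is an assumption. The critical value is the smallest r with P(X ≥ r | N, 0.80) < 0.025.
- N=200: r = 172 (86.0%), actual size 0.0179.
- N=220: r = 188 (85.5%), actual size 0.0232.

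**4. Effect of crediting rescues.** Let 80% of the population have exclusion achieved by the clip, so that rescued subjects fall within the other 20%. Let x be the share rescued and s the share of those scored as excluded. The scored proportion is p = 0.80 + x·s, and the chance of passing is P(X ≥ r | N, p). Both x and s are assumed; s runs from the protocol's 77.5% for other methods up to 100%.

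| x | p (s = 0.775 to 1) | N=200 | N=220 |
|---|---|---|---|
| 0 | 0.800 | 0.018 | 0.023 |
| 1% | 0.808 to 0.810 | 0.033 to 0.040 | 0.043 to 0.052 |
| 2% | 0.816 to 0.820 | 0.059 to 0.081 | 0.077 to 0.104 |
| 5% | 0.839 to 0.850 | 0.239 to 0.391 | 0.298 to 0.471 |

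These shares correspond to 2, 4 and 10 subjects at N=200, and 2.2, 4.4 and 11 at N=220.

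**5. One illustration (assumed counts, N=200).** With 170 clip exclusions, 170/200 = 85.0% and one-sided p = 0.043, so the test is not met. Adding four stapled exclusions gives 174/200 = 87.0% and p = 0.0064, so it is met.

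**6. Away from the null.** At a true rate of 95.7%, power is about 1.0 for N from 150 to 220, with or without the rescued subjects.

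**The case against.** **The LOCF route is inferred.** SAP 5.3 describes LOCF for a subject who misses a scheduled test, and a stapled subject has no 12-month LAA test scheduled. One could conclude that such a subject has no evaluable value. Against that, SAP 5.6.3.1 words LOCF broadly and divides by the total number of subjects. The text is ambiguous, but success is the more natural reading.

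**The stapler TEE may not be an endpoint reading.** Protocol 11.3 lists only Visit 5 and Visit 11 LAA images for the core laboratory, and 5.1.6 judges stapling by residual flow, not by the 3 mm and 10 mm limits. However, endpoint #2 does use Visit 2, and a Visit 5 TEE may exist. A reader might infer that carry-forward of the Visit 2 TEE is certain. The documents support it only as the likely route.

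**The group may be small.** Stapling is limited to anatomical reasons. A subject for whom that decision comes before the clip enters the chest is outside the population, and an imperfectly placed clip is re-opened and re-deployed. This stands: the frequency is unknown and may be low.

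**LOCF is described as conservative.** Protocol 9.8 rests this on the earlier AtriClip trial (98.4% at 3 months against 95.7% at placement). That evidence concerns clips and says nothing about stapled appendages.

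**The endpoint does not decide study success.** Correct: SAP 5.6 ties success to the two primary endpoints. This limits the severity but leaves the scoring gap open.

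**Conclusion.** The gap is real and should be fixed, but it does not threaten study success. Applied as written, the population, numerator, denominator and LOCF rules can count a non-AtriClip closure as an AtriClip success, and nothing in either document prevents it.

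The size depends on an assumed rescue share. At the 80% null, even 1% rescued takes the false-positive rate above the nominal 2.5% (3.3% to 5.2% across the two sample sizes), and 2% takes it to between 5.9% and 10.4%.

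Three stronger readings are not supported:
- A reader might infer error rates of 39% to 47%. Those need true exclusion of exactly 80%, 5% of the population rescued, and every rescue scored as excluded. That 5% exceeds all intra-procedural non-exclusion in the earlier AtriClip trial (3/70 = 4.3%).
- A reader might infer that the test result is in doubt. Near 95.7% it passes either way; what suffers there is the reported rate, which mixes techniques.
- A reader might call this the only labeling test. The documents support only that it is the sole secondary endpoint tested for labeling; both primary endpoints are formally tested as well.

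Keeping attempted subjects in the denominator is sound. Only the scoring rule is missing.

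**What to change.** Add to SAP 5.6.3.1 and Protocol 9.8:

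*A subject in the AtriClip effectiveness population whose final LAA closure is not a deployed AtriClip alone is counted as a failure for LAA exclusion, and no observation made after another exclusion method is carried forward.*

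Apply the same scoring to exploratory endpoint #2, and report exclusion by final closure method so that stapled results remain visible. Settle the rule before analysis, since a choice made afterwards would be open to the charge of being data-driven.

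The cost is small. LAA management details are already recorded at Visit 2 (Protocol 7.2), so no new data and no change in patient care are needed. The exclusion rate falls by the share of such subjects who would otherwise have been scored as excluded. The exact test then keeps its size (0.018 at N=200, 0.023 at N=220). If exclusion by the clip alone is 90% of the population, power is still 0.973 at N=200 and 0.988 at N=220.

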5.3 Handling of Missing Data

All safety analysis will utilize the safety population and no missing values will be imputed unless a subject misses a follow-up visit and cannot subsequently be contacted to determine their primary safety status. In this case, the primary safety endpoint will be considered a failure and the subject will be excluded from any subsequent secondary safety analyses for which their status is unknown. If a procedure is aborted due to a primary safety event, the subject will be considered a safety failure. If a subject misses a follow up visit, but it can be subsequently verified that the subject did not incur a safety failure, the subject will be considered a success. As an additional analysis, the primary safety endpoint will be analyzed based on only observed failures, with all other subjects in the Safety Population counting as a success.

The primary effectiveness analysis will utilize the mITT population and the LOCF method for missing values, as defined below. A subject with any primary effectiveness failure from the 6-month visit

Statistical Analysis Plan		Page 12 of 22
Sponsor	Study	Version
AtriCure	DEEP Pivotal Study	Version 2.0

through the 12-month visit will be considered a failure for all methods below. Any subjects who withdraw or are lost-to-follow-up after the 6-months visit (post AAD optimization) but prior to the 12-month follow-up visit, or for any reason do not have 12-month ECG readings available, will be analyzed as follows:

- 1) Last observation carried forward (LOCF): Any subject who is missing a scheduled testing will be considered an effectiveness success or failure at that scheduled visit based on their status up to and including their last testing.
- 2) Worst case: Any subject with no primary effectiveness failure recorded and with no 12-month test data will be considered a failure.
- 3) Best case: Any subject with no primary effectiveness failure recorded and with no 12-month test data will be considered a success.
- 4) Break-even: If the study endpoint is met using the best-case methodology and is not met using the worst-case methodology, a break-even analysis will be performed to determine the number of subjects with missing endpoint data who would be required to be a success in order to meet the endpoint.

All secondary endpoints for LAA exclusion will utilize the LOCF method for missing values. No missing values will be imputed for the remaining secondary endpoints. If a subject is missing a value for one of these secondary endpoints, they will not be included in the analysis of that endpoint. The number of patients with non-missing values will be reported for each endpoint.

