5.1.2 Study Day

Study day 0 is the date of the index procedure. Day in study will be calculated relative to the index procedure as follows:

$$\text{Study Day} = \text{Assessment Date} - \text{Index Procedure Date}$$

For each subject, duration in study will be based on last study contact date which is the latest date of all follow-up visits, assessments, adverse event onset or resolution, and study exit including date of death.

Duration variables will be calculated as follows:

$$\text{Duration Days} = \text{End Date} - \text{Index Procedure Date}$$

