5.6 Analysis of Study Endpoints

The study will be considered successful if both the primary effectiveness and primary safety endpoints are statistically significant at the 0.025 level (one-sided).

Statistical Analysis Plan		Page 13 of 22
Sponsor	Study	Version
AtriCure	DEEP Pivotal Study	Version 2.0

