5.6.1.1 Primary Analysis

The statistical analysis of the primary effectiveness endpoint will consist of a comparison of the proportion of patients who remain a primary effectiveness success at the 12-month visit to a historical control rate that is based on results from the feasibility trials and published literature. The primary effectiveness endpoint will be assessed with the following hypothesis:

$$H_0: p_E \leq 0.60$$

$$H_a: p_E > 0.60$$

where p_E = the proportion of primary effectiveness success. The hypothesis will be evaluated using a one-sided chi-squared test at a one-sided $\alpha=0.025$ level of significance. The objective will be met if the estimated one-sided p-value is < 0.025. The mITT population will be the primary population for this analysis. Missing values will be treated as described in the Missing Values section 5.3 with the primary method being the LOCF method.

The proportion of primary effectiveness successes will be calculated with subjects as the experimental unit (i.e., the subject will be considered a success if no primary effectiveness failure was recorded from the 6-month visit through the 12-month visit). The numerator of the proportion will be the number of subjects who are a primary effectiveness success, and the denominator will be the total number of subjects. The endpoint will be presented with the numerator and denominator, the proportion and its 95% two-sided exact binomial confidence interval, and the one-sided p-value.

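### For subjects tested between the 6- and 12-month visits who have no 12-month data, the primary LOCF rule coincides with the plan's best case, so late loss can only raise the success rate tested against 60%

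*SAP*

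**What the plan says.** SAP 5.3 names four ways to treat a missing 12-month effectiveness result: LOCF, worst case, best case and break-even. They apply to subjects who leave between the 6- and 12-month visits "or for any reason do not have 12-month ECG readings available". A failure recorded from the 6-month visit through the 12-month visit is a failure under all of them.

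- LOCF: a subject missing a scheduled test "will be considered an effectiveness success or failure at that scheduled visit based on their status up to and including their last testing".
- Best case: "Any subject with no primary effectiveness failure recorded and with no 12-month test data will be considered a success". Worst case scores the same subject as a failure.
- Break-even: if best case meets the endpoint and worst case does not, "a break-even analysis will be performed to determine the number of subjects with missing endpoint data who would be required" to be successes for the endpoint to be met.

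SAP 5.6.1.1 makes LOCF the primary method and defines success: "the subject will be considered a success if no primary effectiveness failure was recorded from the 6-month visit through the 12-month visit". The primary population is mITT (SAP 5.2), whose members must "have at least one post-procedure follow-up visit after the 2nd Blanking Period" with effectiveness data. SAP 5.6 sets the decision rule: "The study will be considered successful if both the primary effectiveness and primary safety endpoints are statistically significant" at one-sided 0.025. Protocol 9.7.1 and 9.9 use the same LOCF rule in the ITT population. Protocol 9.3 allows for roughly 20% attrition among up to 220 treated subjects.

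**The concern.** LOCF reads as a middle course between worst case and best case. For this endpoint it is not. Failure is permanent once recorded, and success is the absence of a record, so a subject who was clean when last tested can carry forward only success.

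Protocol 7.13 and 7.14 schedule 24-hour monitoring in the evaluation window only at the 6- and 12-month visits; in between, rhythm monitoring is symptom-driven. A subject who misses the 12-month test loses one of two scheduled chances for a silent recurrence to be found, and is scored as if that test had been clean.

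The test is against a fixed 60% in a single arm, so no control group shares the upward shift. It goes straight into the error rate of the effectiveness half of the success criterion.

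**Working it through.** **Inputs.** Null rate 0.60, expected rate 0.70, one-sided alpha 0.025, N=182 evaluable, up to 220 treated, about 20% attrition (protocol 9.3). Scoring rules from SAP 5.3 and 5.6.1.1. d and f are assumptions, defined in step 4.

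**1. The plan's own figure.** n = [(1.960·√(0.6·0.4) + 0.842·√(0.7·0.3)) / 0.10]² = 181.1, which rounds up to the stated 182. This is without the continuity correction that protocol 9.3 mentions; with it, n is 192. That is a separate matter and does not affect this point.

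**2. Scoring of subjects tested in the window.**

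| Failure recorded | 12-month data | LOCF | Best case | Worst case |
|---|---|---|---|---|
| yes | yes | failure | failure | failure |
| yes | no | failure | failure | failure |
| no | yes | success | success | success |
| no | no | success | success | failure |

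LOCF and best case agree in every row. Enumerating 48 combinations of 3-month rhythm, 6-month test, symptom-driven test and non-ECG failure gives no case where they differ. They can differ only when nothing was tested from the 6-month visit on: the last test may be a 3-month ECG showing arrhythmia, or there may be no earlier test, and the SAP does not say what status is then carried. No direction is claimed for those subjects.

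**3. Threshold at N=220.** P(X ≥ 147 | 220, 0.60) = 0.0221 and P(X ≥ 146) = 0.0307, so the protocol's exact test needs 147 (66.8%). For the SAP's chi-squared test without correction, z = (147/220 − 0.60)/√(0.24/220) = 2.06 passes and 146 (z = 1.93) does not. The tests share one threshold. At N=198 it is 133 (size 2.25%).

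**4. Error when the true rate is 60%.** Let d be the share of the analysed set lost after 6-month testing, and f the share of the lost subjects' true failures already recorded before loss. With loss unrelated to outcome, the apparent success rate is 0.60 + 0.40·d·(1 − f). The chance of falsely meeting effectiveness is then P(X ≥ 147 | 220):

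| d | f=0.9 | f=0.75 | f=0.5 |
|---|---|---|---|
| 5% | 2.5% | 3.1% | 4.4% |
| 10% | 2.9% | 4.4% | 7.9% |
| 20% (ceiling) | 3.8% | 7.9% | 21% |

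Example: d=10%, f=0.75 gives 0.60 + 0.40·0.10·0.25 = 0.610 and 4.4%. If half of 44 losses (20% of 220) fall before mITT entry, then N=198 with 22 late losses, and the three values are 3.0, 4.6 and 8.5%.

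**5. Illustration.** Suppose 125 of 198 completers succeed, and 22 further subjects are failure-free when last tested but have no 12-month data.

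- LOCF and best case: (125 + 22)/220 = 147/220 = 66.8%. Effectiveness is met.
- Worst case: 125/220 = 56.8%.
- Imputing the 22 from completers who were still failure-free: 73 completers failed. If a share e of those failures was recorded early, the chance of remaining a success is 125/(125 + 73(1 − e)). For e=0.5 this is 0.774, giving 125 + 17.0 = 142.0. For e=0.9 it is 0.945, giving 125 + 20.8 = 145.8. So about 142 to 146 of 220 (64.6 to 66.3%), with one-sided p about 0.09 to 0.03 before any allowance for imputation variance. Effectiveness is not met.

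**The case against.** The strongest reply is that the plan does not hide this. Worst case and break-even are prespecified, and break-even is triggered exactly when best case passes and worst case fails. ITT and PP repeats (SAP 5.2) and visit-level accountability (SAP 5.4) are planned too. A reader of the report would see any dependence on missing data. All of that stands, and a reader who infers that sensitivity analyses are lacking would be wrong. What remains is that none of them bears on whether the endpoint is met: the ITT and PP repeats change the population rather than the scoring rule, and break-even reports a count with no stated consequence.

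It is also fair that d and f are assumed and that f may be high. Besides 6-month monitoring, failures can be recorded through the symptom-driven monitor, cardioversion, drug changes and re-ablation (SAP 2.1.1). That argues for leading with the lower part of the table.

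Four stronger readings are tempting and are not supported:

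- That LOCF equals best case for everyone. It does so only for subjects tested in the window.
- That a later clean test can erase an earlier failure. SAP 5.3 rules this out.
- That the illustration should be set against the completers alone (125/198 = 63.1%, exact p = 0.20). The 22 were failure-free when last seen, so their expected success exceeds that of all completers.
- That error reaches 21%. That takes d=20% together with f=0.5, while the protocol's 20% covers all attrition, including losses before mITT entry.

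**Conclusion.** The concern holds for subjects tested in the 6-to-12-month window who have no 12-month data. For them the primary analysis sits at the favourable end of the plan's own sensitivity range, and missing data can only move the estimate up relative to complete follow-up. This follows from the definitions and needs no outside figure.

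The size is less certain. With N=220, a true rate of 60% and loss unrelated to outcome, false success on the effectiveness test rises from 2.2% to about 2.5 to 4.4% for d of 5 to 10% and f of 0.75 to 0.9, and to 7.9% at d=10% and f=0.5. These figures concern effectiveness alone; study success also needs the safety endpoint. If late loss is small or most failures are recorded early, the effect is slight. It should be fixed before analysis, because the stated one-sided 0.025 is not assured under the primary rule.

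**What to change.** In SAP 5.3 and 5.6.1.1, and to match in protocol 9.7.1 and 9.9, replace LOCF as the primary method with prespecified multiple imputation of 12-month status:

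1. Every recorded failure stays a failure.
2. Subjects with no recorded failure and no 12-month data are imputed from subjects still failure-free at a comparable point of follow-up. Do not use all completers, and do not condition on a clean 6-month result alone, which ignores later failure-free time and biases the estimate down. Follow-up dates already exist: SAP 5.1.2 says that "duration in study will be based on last study contact date".
3. The lower one-sided 97.5% limit is compared with 60%.
4. State one time scale for ordering scheduled tests and between-visit events. SAP 5.1.3 analyses visits by nominal label, whereas cardioversions and drug changes carry dates. For subjects without an endocardial procedure, time follow-up from surgery, as protocol 9.2.1 does.
5. Say how subjects with no test in the evaluation window are handled.
6. Make baseline covariates optional unless the list is fixed (SAP 5.7 leaves the comorbid conditions open) and the procedure with them is checked by simulation.

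Keep worst case, best case and break-even as sensitivity analyses. Add a delta or tipping-point analysis, because imputation holds the error rate only if loss is unrelated to the unseen outcome.

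The cost is wording and modest programming, with no new data. The estimate will be less favourable and power lower than under LOCF. For orientation, complete-case exact power at a true 70% is 83% with n=198 and 78% with n=176. A simulation of the imputation gave false success of 2.3 to 2.5% and power of 82 to 88% at N=220 under loss unrelated to outcome. Under informative loss, false success was 5.7 to 10.5%, against 8.0 to 21.4% for LOCF. That simulation used no covariates and has not been independently reproduced, so it should be rerun on the final specification.
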